1 INTRODUCTION

Apixaban is a novel, orally active, potent, direct selective inhibitor of coagulation FXa that directly and reversibly binds to the active site of FXa and exerts anticoagulant and antithrombotic effects by diminishing the conversion of prothrombin to thrombin. Apixaban is currently indicated to reduce stroke and systemic embolism in patients with nonvalvular atrial fibrillation, for the treatment of deep venous thrombosis (DVT), and for the prophylaxis of DVT in patients who have undergone hip or knee replacement surgery. Apixaban is not indicated for the treatment of atrial fibrillation caused by valvular heart disease or for patients with mechanical prosthetic valves requiring chronic oral anticoagulation.

Patients undergoing coronary artery bypass grafting (CABG) are at risk for the development of postoperative atrial fibrillation (POAF). POAF adversely impacts patient outcomes, and patients who develop POAF are at increased risk for stroke or thromboembolic complications, with an increased duration of hospitalization. Usually occurring in the early postoperative period and usually short-lived, POAF requires anticoagulation when persistent or recurrent. Duration of therapy for POAF is typically short-term, as POAF is usually short-term and self-limiting over 3-4 weeks.

Warfarin therapy has been the mainstay of therapy for patients with POAF. While the duration of therapy is usually short (3-4 weeks), complications of anticoagulation do occur. Additionally, warfarin therapy for POAF is associated with increased length of stay, need for monitoring, and bleeding complications.

Apixaban has been demonstrated to be superior to warfarin for the reduction of stroke or systemic embolism in patients with non-valvular atrial fibrillation. Additionally, major bleeding was significantly reduced in patients receiving apixaban compared to warfarin. The use of apixaban in patients with POAF has not been well studied, however, and whether these benefits will be seen in patients with POAF is unclear. In this small prospective pilot study, we aim to compare apixaban and warfarin anticoagulation strategies for the outcomes of venous thromboembolism/stroke and bleeding events when utilized in patients with new-onset postoperative atrial fibrillation after isolated coronary artery bypass grafting (CABG).

1.1 Scientific or Scholarly Background

Post-operative atrial fibrillation is defined as atrial fibrillation of new onset in the immediate post-operative period. Published rates of POAF after cardiac surgery is traditionally 20-30%, which is similar to rates observed at our facility.¹⁻⁴ Patients at the highest risk for POAF are those of advanced age; for each 10-year increase in age, the odds of developing atrial fibrillation after surgery increase by 75%.⁵ Other patients at increased risk for developing POAF are those with a history of smoking, hypertension, or congestive heart failure, as well as patients undergoing urgent or emergent coronary artery bypass graft surgery. While atrial fibrillation occurs at any time after cardiac bypass surgery, it is most common within four days of surgery, and the peak incidence is on post-operative day two.⁵ For persistent POAF, the American College of Cardiology, American Heart Association, and European Society of Cardiology recommend anticoagulation if rate-control measures and cardioversion therapy fail to return the patient to normal sinus rhythm.⁶ In addition to warfarin, there are four novel anticoagulants approved for the management of non-valvular atrial fibrillation: apixaban, rivaroxaban, edoxaban, and dabigatran etexilate mesylate. Apixaban, rivaroxaban, and edoxaban are FDA approved for prophylaxis of cerebrovascular accidents and systemic thromboembolisms in the maintenance of atrial fibrillation.^{7,8} Dabigatran is FDA approved for prophylaxis of thromboembolic disorders in patients with atrial fibrillation⁹. These novel agents have well-established safety and efficacy profiles, but have not been well studied for atrial fibrillation due to reversible causes such as POAF, or immediately after a major surgery such as a CABG. The ARISTOTLE study excluded patients with atrial fibrillation due to reversible causes such as surgery, and the RE-LY and ROCKET AF trials excluded patients with an increased risk of bleeding, including those that underwent major surgery in the previous 30 days, as well as patients with atrial fibrillation due to reversible causes, specifically cardiac surgery.¹⁰⁻¹²

1.2 Overall Risk/Benefit Assessment

Patients experiencing POAF after undergoing isolated CABG that require anticoagulation are currently placed on warfarin with a goal INR of 2-3. Compared to the current standard of care, apixaban may offer similar or improved safety and efficacy profiles, and this pilot study may provide a valuable signal of benefit and safety for apixaban use in the setting of POAF.

1.3 Research Hypothesis

In this pilot study, we hypothesize that there will be no significant differences between apixaban and warfarin anticoagulation strategies for the outcomes of venous thromboembolism/stroke or bleeding events, when utilized for new-onset postoperative atrial fibrillation after isolated coronary artery bypass grafting (CABG). This small prospective pilot study will not likely be adequately powered to show statistically significant differences in safety or efficacy between patients treated with apixaban or warfarin.

1.4 Study Rationale

Post-operative atrial fibrillation is defined as atrial fibrillation of new onset in the immediate post-operative period. Published rates of POAF after cardiac surgery is traditionally 20-30%, which is similar to rates observed at our facility.^{2,4-6} Patients at the highest risk for POAF are those of advanced age; for each 10-year increase in age, the odds of developing atrial fibrillation after surgery increase by 75%.⁷ Other patients at increased risk for developing POAF are those with a history of smoking, hypertension, or congestive heart failure, as well as patients undergoing urgent or emergent coronary artery bypass graft surgery. While atrial fibrillation occurs at any time after cardiac bypass surgery, it is most common within four days of surgery, and the peak incidence is on post-operative day two.⁷ For persistent POAF, the American College of Cardiology, American Heart Association, and European Society of Cardiology recommend anticoagulation if rate-control measures and cardioversion therapy fail to return the patient to normal sinus rhythm.⁸ In addition to warfarin, there are four novel anticoagulants approved for the management of non-valvular atrial fibrillation: apixaban, rivaroxaban, edoxaban, and dabigatran etexilate mesylate, although none of these have been studied in patients with POAF. Apixaban is indicated as follows:

INDICATIONS AND USAGE-----

ELIQUIS is a factor Xa inhibitor indicated:

- to reduce the risk of stroke and systemic embolism in patients with nonvalvular atrial fibrillation. (1.1)
- for the prophylaxis of deep vein thrombosis (DVT), which may lead to pulmonary embolism (PE), in patients who have undergone hip or knee replacement surgery. (1.2)
- for the treatment of DVT and PE, and for the reduction in the risk of recurrent DVT and PE following initial therapy. (1.3, 1.4, 1.5).¹

Rivaroxaban, and edoxaban are FDA approved for prophylaxis of DVT and prevention of pulmonary embolism and for the reduction of stroke and systemic thromboembolism in patients with nonvalvular atrial fibrillation.^{9,10} Dabigatran is FDA approved for prophylaxis of thromboembolic disorders in patients with atrial fibrillation¹¹. These novel agents have well-established safety and efficacy profiles, but have not been well studied for atrial fibrillation due to reversible causes such as POAF, or after major

surgery such as a CABG. The ARISTOTLE study excluded patients with atrial fibrillation due to reversible causes such as surgery, and the RE-LY and ROCKET AF trials excluded patients with an increased risk of bleeding, including those that underwent major surgery in the previous 30 days, as well as patients with atrial fibrillation due to reversible causes, specifically cardiac surgery.¹²⁻¹⁴

2 STUDY OBJECTIVES

2.1 Primary Objective

- 1) Efficacy: Venous thromboembolism or stroke, followed until postoperative day 30.
- 2) Safety: major and minor bleeding events, followed until postoperative day 30, as defined by the International Society on Thrombosis and Haemostasis³
- 3) Clinical relevant non-major bleed.
- 4) Transfusions: units of blood or blood products given after the first dose of anticoagulation.
- 5) Total post-operative length of stay in days, defined as the time the patient leaves the operating room (day 0) until hospital discharge. Length of stay will increase by 1 day with each midnight that is passed.
- 6) Time in therapeutic range of INR, if on warfarin, (eg. 2-3), measured as a percentage and defined for each patient using the Rosendaal equation.
- 7) Patient compliance percentage to apixaban dosing, calculated as a percentage using the following equation
 - a. $(\# \text{ doses prescribed} - \# \text{ of doses not taken and returned to investigator at follow up appointment}) / \# \text{ doses prescribed}$; the follow up visit will occur after anticoagulation prescription has ended.

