Study Objectives:	
1) Primary endpoint: freedom from stroke or thromboembolic event will be captured.
 
2) Secondary endpoints: -units of blood given after initiation of anticoagulation medication -total post-operative length of stay -duration from diagnosis of post-operative atrial fibrillation (POAF) to discharge from hospital -time in therapeutic range of INR if on warfarin -patient compliance percentage to apixaban if on apixaban
 
3) Safety assessments: major and minor bleeding events, as defined by the International Society on Thrombosis and Haemostasis, will be captured. Clinical events and blood product utilization will be identified and captured.

Study Design:	
In this open-label, prospective, randomized pilot study, patients who develop atrial fibrillation after isolated coronary artery bypass grafting surgery will be identified. Patients with persistent atrial fibrillation (>12 hours) or recurrent sustained atrial fibrillation (≥ 2 episodes of atrial fibrillation lasting longer than 30 minutes) will be candidates for inclusion. Upon meeting study inclusion and exclusion criteria, and after informed consent, patients will be randomized to either the standard of care (warfarin per protocol) or apixaban arms of the trial. Routine postoperative care after CABG will occur in both groups. Upon discharge, anticoagulation in both groups will be managed by the anticoagulation clinic. Patients will be followed for 30 days after surgery.

Accrual Goal: (Total number of subjects)	56 patients
Accrual Rate: (Number of subjects expected per month)	We anticipate enrolling 2-3 patients per month based on current projections.
FPFV: LPFV: Follow Up: (mm/dd/yy)	FPFV: 9/1/16 LPFV: 12/31/18 Follow up: 30 days per patient Final Report: 3/31/19

Correlative Studies: (PK/PD, etc.)
	
Retrospective analysis conducted at our facility:
 
Anderson E, Johnke K, Leedahl D, Dyke, C. Novel oral anticoagulants vs warfarin for the management of postoperative atrial fibrillation: clinical outcomes and cost analysis. American Journal of Surgery. Volume 210, Issue 6, 1095-1103²

Inclusion Criteria:
	
Patients diagnosed with new-onset persistent or recurrent atrial fibrillation after isolated CABG surgery. Persistent atrial fibrillation is defined as an episode of >12 hours. Recurrent atrial fibrillation is defined as 2 or more episodes of atrial fibrillation lasting longer than 30 minutes.

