4 INVESTIGATIONAL PLAN

4.1 Study Design and Duration

Planned study design: prospective, controlled, randomized pilot study

Screening procedures/study population: Patients will be eligible for screening if they develop atrial fibrillation in the postoperative period that:

1. Persists 12 hours or more.
2. Develop recurrent atrial fibrillation with two or more episodes of persistent AFib of at least 30 minutes duration during the same hospital stay.

Number of subjects per arm: 28

Randomization ratio/method: 1:1, determined in permuted block fashion

Duration of treatment: 30 days of oral anticoagulation therapy. This period will start with the first dose of anticoagulation (either apixaban or warfarin) given in the hospital, and continue until the patient's 30-day post-operative appointment.

Criteria for evaluation:

- Efficacy: systemic thromboembolism or stroke will be assessed retrospectively after the patient has completed the 30-day course of therapy.
 - Events relating to thromboembolism or stroke will be adjudicated using pre-determined definitions by independent committee members that remain blinded to the patient's treatment arm.
- Safety: major bleeding will be as defined by the Society on Thrombosis and Haemostasis, as follows:
 - 1. Fatal bleeding, and/or
 - 2. Symptomatic bleeding that occurs in a critical area or organ, such as intracranial, intraspinal, intraocular, retroperitoneal, pericardial, in a non-operated joint, or intramuscular with compartment syndrome, assessed in consultation with the surgeon, and/or
 - 3. Extrasurgical site bleeding causing a fall in hemoglobin level of 20 g/L (2g/dL) or more, or leading to transfusion of two or more units of whole blood or red cells within 24-48 hours of the bleeding and/or
 - 4. Surgical site bleeding that requires a second intervention – open, arthroscopic, endovascular- or a hemarthrosis of sufficient size as to interfere with rehabilitation by delaying mobilization or delayed wound healing, resulting in prolonged hospitalization or a deep wound infection, and/or
 - 5. Unexpected surgical site bleeding, prolonged and/or sufficiently large to cause hemodynamic instability, as assessed by the surgeon, with a fall in hemoglobin of at least 20 g/L (2g/dL) or transfusion of two or more units of whole blood or red cells within 24 hours of the bleeding.³

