5.7 Treatment Compliance

Patient compliance will be monitored during the study. While the patient is hospitalized, we will monitor whether apixaban or warfarin is given as directed by the study coordinator. After the patient has been discharged from the hospital, apixaban compliance will be measured by asking the patient to bring any unused medication to their 30-day post-operative appointment, where remaining tablets will be counted. As 60 tablets will be dispensed to each patient (30-day supply), we use the following formula:

$$[(60 - (\text{\# of remaining tablets})) * 100] / [2 * (\text{days since filled})] = \text{percent compliance.}$$

After hospital discharge, warfarin compliance will be monitored by measuring the time in therapeutic INR range (2-3).

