6 STUDY ASSESSMENTS AND PROCEDURES

6.1 Time and Events Schedule

If a subject chooses to be removed from the study, withdraws informed consent, or if therapy must be stopped in the interest of the patient's safety, data collected to that point of the study will be collected for intent-to-treat analysis. We will document the reason for a patient's early withdrawal from the study, or the discontinuation of treatment for a patient by the patient's physician or study coordinator.

After the 30-day post-operative physician examination, there will be no further patient assessments. Analysis of all outcomes will be done by EMR analysis, except for treatment compliance as noted above.

Time and Events Schedule for Protocol: CV185-505

Procedure	Prior to Surgery (day of surgery, or <30 days prior)	After Diagnosis of AFib	Upon Hospital Discharge	At Each Anticoagulation Clinic Visit (warfarin)	At 30-Day Post-Operative Examination	After 30-Day Post-Operative Examination
Eligibility Assessments						
Informed Consent		X				
Medical History		X				
Inclusion/Exclusion Criteria		X				
Clinical Drug Supplies						
Randomize		X				
Dispense Study Treatment			X			
Patient Medication Consultation			X			
Safety Assessments						
Pregnancy Test for WOCBP	X					
Renal Function Test	X	X				
Hepatic Function Test		X				
INR measurement	X	X		X		
Monitoring for Bleeding Events			X	X	X	
Monitoring for Thrombotic Events			X	X	X	
Efficacy Assessments						
Measure Apixaban Adherence					X	
EMR Analysis of All Other Outcomes						X
Outcomes Statistical Analysis						X

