6.4.2 Secondary Assessments

- 1) Units of blood or blood products given after the first dose of anticoagulation.
- 2) Total post-operative length of stay: This will be measured from the date/time of the end of the subject's surgery until the date/time of the patient's discharge from the hospital. This will be measured in hours, to the nearest tenth of an hour.
- 3) Duration from diagnosis of post-operative atrial fibrillation (POAF) to discharge from the hospital: This will be measured from the time of the EKG that is obtained after AFib is noted on telemetry (confirming the diagnosis of AFib), until hospital discharge. This will be measured in hours, to the nearest tenth of an hour.
- 4) Time in therapeutic range of INR, if on warfarin, (eg. 2-3), measured as a percentage and defined for each patient using the Rosendaal equation
- 5) Patient compliance percentage to apixaban: measured by asking the patient to bring any unused medication to their 30-day post-operative appointment, where remaining tablets will be counted. This will be calculated as a percentage using the following

equation: (# doses prescribed - # of doses not taken and returned to investigator at follow up appointment) / # days prescribed.

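### Section 2.1's apixaban compliance formula counts tablets not yet due as missed: if 60 tablets filled at discharge on day D are counted on post-operative day 30, full adherence scores only 1 − D/30

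*Combined protocol and SAP*

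**What the plan says.** The protocol gives three formulas for the same measure.

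- **Section 2.1, item 7:** the numerator is doses prescribed minus the number "of doses not taken and returned to investigator at follow up appointment"; the denominator is doses prescribed. The item adds that "the follow up visit will occur after anticoagulation prescription has ended".
- **Section 5.7:** "As 60 tablets will be dispensed to each patient (30-day supply), we use the following formula": 60 minus remaining tablets, times 100, over twice the days since filling. In-hospital administration is monitored separately, so the tablet count covers the time after discharge.
- **Section 6.4.2, item 5:** the same numerator as section 2.1, divided by the number of days prescribed. Compliance is "measured by asking the patient to bring any unused medication to their 30-day post-operative appointment, where remaining tablets will be counted".

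On timing, the schedule in section 6.1 marks "Dispense Study Treatment" in the hospital-discharge column. Section 5.7 asks patients to "bring any unused medication to their 30-day post-operative appointment, where remaining tablets will be counted". That appointment is timed from surgery; the synopsis says "Patients will be followed for 30 days after surgery".

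The documents do not agree on when treatment ends. The synopsis has anticoagulation stopping when no longer needed, typically within 30 days of surgery. Section 4.1 describes 30 days from the first in-hospital dose, but also has treatment "continue until the patient's 30-day post-operative appointment". Section 5.4 says at least 30 days.

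**The concern.** The section 2.1 formula is sound only if the whole supply has fallen due by the time it is counted. Here the supply clock starts at discharge and the count clock starts at surgery. A 30-day supply filled on post-operative day D runs to day 30 + D, so on day 30 about D days of tablets are properly still in the bottle. Section 2.1 subtracts them in the numerator and keeps them in the denominator. This happens to a patient who follows every instruction and returns every tablet.

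The score also becomes tied to length of stay, which is another endpoint: of two patients with identical tablet-taking, the one who goes home later scores lower. Section 9.1 offers the pilot as a reference for future studies, so an adherence figure that is low for this reason could be carried forward.

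**Working it through.** The plan states no expected compliance value, so there is no figure to reproduce.

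**Inputs from the documents:** 60 tablets, two per day (sections 5.4 and 5.7; the same number at either strength); dispensed at discharge (section 6.1); counted at the 30-day post-operative appointment (sections 5.7 and 6.4.2).

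**Assumptions:** filled on the day of discharge, D; counted on post-operative day 30; doses prescribed means the 60 tablets and days prescribed means 30; D from 4 to 10 for illustration.

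**Full adherence.** Doses due and taken by day 30 = 2(30 − D). Tablets returned = 60 − 2(30 − D) = 2D.

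- Section 2.1: (60 − 2D)/60 = 1 − D/30
- Section 5.7: (60 − 2D)/[2(30 − D)] = 1
- Section 6.4.2: (60 − 2D)/30

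| D | Taken | Returned | Section 2.1 | Section 5.7 | Section 6.4.2 |
|---|---|---|---|---|---|
| 4 | 52 | 8 | 52/60 = 86.7% | 52/52 = 100% | 52/30 = 173.3% |
| 6 | 48 | 12 | 48/60 = 80.0% | 48/48 = 100% | 48/30 = 160.0% |
| 8 | 44 | 16 | 44/60 = 73.3% | 44/44 = 100% | 44/30 = 146.7% |
| 10 | 40 | 20 | 40/60 = 66.7% | 40/40 = 100% | 40/30 = 133.3% |

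**Partial adherence.** A patient who takes 80% of due doses scores 0.8 × 52/60 = 69.3% at D = 4 and 0.8 × 40/60 = 53.3% at D = 10 under section 2.1, against 80% under section 5.7.

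**Visit on day V instead of day 30.** The section 2.1 score at full adherence is min[60, 2(V − D)]/60. On day 35 it is 100%, 96.7%, 90.0% and 83.3% for D = 4, 6, 8 and 10; on day 40 it is 100% for all four. The shortfall vanishes when V − D is at least 30.

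**Other readings of doses prescribed.**

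- Adding in-hospital doses from a first dose on day S gives a denominator of 60 + 2(D − S), with 2D still returned. For S = 2, D = 4 this is 56/64 = 87.5%; for S = 4, D = 10 it is 52/72 = 72.2%.
- Taking it as doses due from discharge to the visit, with all leftovers still subtracted, gives (30 − 2D)/(30 − D): 22/26 = 84.6% at D = 4 and 10/20 = 50% at D = 10.

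**Early stop on day E, on a physician's direction, all due doses taken.** Taken = 2(E − D). Section 2.1 gives (E − D)/30 and section 5.7 gives (E − D)/(30 − D); both are below 100% for E before day 30.

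**Limit of section 5.7.** Its denominator has no cap. For D = 4 and a count on day 40, a patient who took all 60 tablets scores 60/(2 × 36) = 60/72 = 83.3%.

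**The case against.** The strongest reply is that section 5.7, which deals with treatment compliance, already has a denominator that removes the bias on a day-30 count; the harm arises only if the analyst uses section 2.1. That stands as far as it goes, and it means this should be settled together with the disagreement among the three formulas. But nothing ranks section 5.7 above the objectives section, and a sponsor asked merely to harmonise could choose the section 2.1 version.

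A second reply is that the premise in section 2.1 may be true, since the synopsis has treatment typically ending within 30 days of surgery. A reader might infer that the timetable simply refutes section 2.1. The documents do not support that: they conflict on when treatment ends. Yet an early stop does not rescue the formula, because the unused tablets are still returned and still counted as missed.

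A third reply is that section 2.1 never says 60, and that doses not taken could mean only missed doses, leaving out those not yet due. The wording is open to this. Full adherence would then score 100%, but with 60 as denominator partial adherence would be overstated: at D = 4 the 80% patient misses 0.2 × 52 = 10.4 doses and scores 49.6/60 = 82.7%. A count of returned tablets also cannot separate missed from not yet due without the fill date, which section 2.1 does not use.

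Finally, simply copying section 5.7 elsewhere would exchange one bias for another when the visit is late. That is correct, and it is why the denominator needs a cap.

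**Conclusion.** The concern holds in conditional form. With 60 tablets filled at discharge on day D, a count on post-operative day 30 and doses prescribed read as those 60, section 2.1 understates full adherence by D/30. It does not do so if the count comes at least 30 days after the fill.

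Three stronger inferences are not supported.

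- A reader might take 66.7% to 86.7% as the expected result. It rests on an assumed discharge on days 4 to 10 and an exact day-30 visit; the documents give neither.
- A reader might say the score measures discharge day rather than adherence. It still falls with missed doses (86.7% to 69.3% at D = 4); it is biased by discharge day, not replaced by it.
- A reader might say the trial would report adherence as poor. The documents set no adherence threshold.

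The reach is limited. The measure is descriptive and confined to the apixaban arm (28 patients planned). It sits under the Primary Objective heading in section 2.1 but is secondary in the synopsis and section 6.4.2. The primary endpoint and the sample size do not depend on it.

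**What to change.** Use one formula in sections 2.1, 5.7 and 6.4.2:

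100 × (60 dispensed − tablets returned) / min[60, 2 × days from the fill date to the earlier of the count date and any physician-directed stop].

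At full adherence this gives 52/52 = 100% for D = 4 with a day-30 count, 60/60 = 100% for D = 4 with a day-40 count, and 2(E − D)/[2(E − D)] = 100% after a directed stop on day E.

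Remove the statement in section 2.1 that the visit follows the end of the prescription, or reconcile it with the synopsis and sections 4.1 and 5.4 on when treatment ends. Which account of treatment duration applies is for the investigators to settle; the formula needs only the dates.

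The cost is a wording change. Section 5.7 already requires the fill date and the tablet count at a dated visit. Section 6.1 already has the reason for a physician's discontinuation documented, and the date should be recorded with it. No visit or procedure is added.
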